6 STUDY DEVICE AND TREATMENT OF SUBJECTS

6.1 Description of the study device

Belotero Balance is a sterile, bioresorbable, non-pyrogenic, viscoelastic, clear, colorless, homogeneous gel device. Belotero Balance is a bacterially fermented, injectable, hyaluronic-acid-based dermal filler. After extraction and purification, hyaluronic acid manufactured from streptococcal cultures is cross-linked with a binding agent 1,4-butanediol diglycidyl ether (BDDE) in two consecutively executed reactions and reconstituted in a physiologic buffer at pH 7 and concentration of 22.5 mg/mL.

6.2 Usage

Belotero Balance should be used in the IOH treatment region according to the information and injection instructions presented in [Section 6.3.3](#). Additional information on product usage is provided in [Appendix 10.3](#).

6.3 Study treatment

All protocol-specific criteria for the administration of study treatment must be met and documented prior to administration of any study treatment. Study treatment (injection) will be administered only to eligible subjects by a qualified oculoplastic surgeon. Subjects will not be dispensed any investigational material. Any noncompliant subject or site may be discontinued from the study ([Section 5.2](#)).

6.3.1 *Planned treatment procedure and administration*

[figure not shown]
Approximately 44 subjects will be randomized to receive treatment and 22 subjects will serve as the controls. Subjects will be randomized using a 2:1 allocation ratio for treatment to control.

For subjects randomized to the treatment group, both right and left IOHs will receive treatment with Belotero Balance per the administration instructions specified below.

6.3.2 *Infraorbital hollow treatment region*

Belotero Balance is to be deposited in the suprperiosteal plane. Injection volume will be recorded. [Figure 3](#) illustrates the region of the IOH that may be treated. The infraorbital treatment area is at the junction of the lower eyelid and mid-face where a volume deficit has formed. The area is bordered by the nasal sidewall medially, the temporal region of the bony orbit laterally, the bulk of the lower eyelid superiorly, and the superior aspect of the mid-face inferiorly.

Figure 3: Treatment region

6.3.3 *Injection procedure*

6.3.3.1 *Preparation of the injection region*

- Any makeup in the IOH area should be removed.
- As with all transcutaneous procedures, Belotero Balance injection carries a risk of infection and should be conducted with aseptic technique.
- Only topical anesthetic, at the preference of the treating physician, or ice may be applied. Any medication or therapy must be recorded in the CRF.

6.3.3.2 *Directions for use of cannula*

[figure not shown]
1. To attach the cannula to the syringe, open the cannula packaging to expose the hub. Use only the cannula provided with the clinical trial supply.
2. Remove the Luer lock syringe cap from the distal end of the syringe prior to attaching the cannula (see [Figure 4](#)).

Figure 4: Removing the Luer lock syringe cap from the syringe

[figure not shown]
3. Holding the Luer lock fitting of the syringe, twist the cannula onto the syringe. The cannula must be tightened securely to the syringe. Do not over-tighten as this may break the cannula and/or dislodge the syringe (see [Figure 5](#)).

Figure 5: Placing the needle or cannula onto the syringe

4. Pull off the cannula guard to expose cannula (see [Figure 6](#)).

Figure 6: Removing the cannula guard

5. Prime the cannula with Belotero Balance.
6. If excess implant is on the surface of the Luer lock fitting, it will need to be wiped clean with sterile gauze. Slowly push the syringe plunger until the implant material exudes from the end of the cannula. If leakage is noted at the Luer lock fitting, it may be necessary to remove the cannula, clean the surfaces of the Luer lock fitting, and reattach the cannula. In extreme cases, replace both the syringe and the cannula.

6.3.3.3 *Depth of injection and injection technique*

Standard precautions associated with injectable materials should be followed.

- The cannula injection technique of Belotero Balance with regard to the angle and orientation of the bevel, the depth of injection, and the quantity administered may vary. Fewer injection points are usually used when a cannula is utilized instead of a needle. Insertion sites will typically be at the malar and zygomatic regions. For insertion of the cannula, first a skin puncture should be made at the desired insertion point using the provided needle. The needle will be of slightly larger gauge than the cannula. After the needle is withdrawn the cannula will be inserted through the established skin puncture. Subsequently, a tunneling, fanning, or combination injection technique will be used to achieve optimal results. Care must be used to avoid intravascular injection regardless of technique used.
- In general, when the needle and then cannula are inserted, it will be at an approximate angle of 30° or less parallel to the skin. Belotero Balance will be placed at the junction of the lower eyelid and midface along the inferior orbital rim in the supraperiosteal plane. The injection should be performed with a constant low-to-moderate pressure on the plunger, while slowly and gradually withdrawing the cannula. Slight elevation of the skin should be observed without significant blanching of the skin. To avoid visible lumps and/or discoloration,

avoid injection of Belotero Balance superficially when removing the cannula. When the injection is complete, the site may be gently massaged, if necessary.

6.3.3.4 *Additional injection information*

- If blanching occurs, the injection should be stopped and the area massaged until it returns to a normal color. Blanching may be a sign of a vascular occlusion. If normal skin coloring does not return, do not continue with the injection. Treat in accordance with the American Society for Dermatologic Surgery guidelines, which include possible hyaluronidase injection.
- Correct to the desired volume effect. Do not overcorrect. The degree and duration of the correction depend on the character of the defect treated, the tissue stress at the implant site, the depth of the implant in the tissue, and the injection technique. Markedly indurated defects may be difficult to correct.
- Follow national, local, or institutional guidelines for use and disposal of medical sharp devices. To help avoid needle or cannula breakage, do not attempt to straighten a bent needle or cannula. Discard it and complete the procedure with a replacement needle from the clinical supply. Do not reshield used needles and cannulas. Recapping by hand is a hazardous practice and should be avoided. Discard unshielded needles and cannulas in approved sharps containers. For additional product handling information, see [Section 6.2](#).

6.3.3.5 *Post-treatment care/pain management*

- To manage pain, once the injection is complete ice may be applied as needed.
- Acetaminophen may be taken if instructed by the physician. Any medication or therapy used by the subject must be recorded in the CRF.
- The following information should be shared with subjects:
 - Within the first 24 hours, subjects should avoid lower eyelid makeup, strenuous exercise, extensive sun, or heat exposure, aspirin or non-steroidal anti-inflammatory drugs and alcoholic beverages. Exposure to any of the above may cause temporary redness, swelling and/or itching at the injection site.
 - Any and all medications used throughout study participation should be reported by the subject to site personnel for recording in the CRF.

6.3.4

6.3.5 *Packaging of treatment supplies*

The following components are supplied for the injection procedure:

- Belotero Balance box containing one sterile 1-mL prefilled glass syringe of Belotero Balance with two 27G $\frac{1}{2}$ " or 30G $\frac{1}{2}$ " needles.

More than one Belotero Balance box may be used depending on injection volume.

- A peel-off patient label, indicating product, to be placed in the source documents.
- A separate bulk supply of 27G 40 millimeter (mm) blunt-tipped cannula with a 25G pre-hole needle will be sent for the injection procedure.

6.3.6 *Receipt, storage, dispensing, and return/disposal*

Upon receipt, the site personnel will verify the contents of all study supplies received and promptly notify the appropriate contacts of any discrepancies or damages. The investigator is responsible for ensuring that an accurate record of inventory is maintained. The investigator will keep a current record of the study product delivery to the study site, inventory, and dispensing, and this record will be made available to the sponsor upon request. Study sites will be queried about any discrepancies.

All study devices must be stored in a secure, environmentally controlled, and monitored area in accordance with the labeled storage conditions.

Only authorized study personnel may supply, dispense, or administer study treatment, and only subjects enrolled in the study may receive study treatment. The investigator is responsible for maintaining a current, accurate record of all study treatment dispensation.

Any used syringes of Belotero Balance, pre-hole needles, and cannulas should be discarded per the appropriate handling and disposal procedures at the site. Any unused/unopened product, needles/cannulas and outer packaging (of used kits) should be retained for the monitor to perform device accountability procedures.

At the end of the study and after verification of study device kit accountability, it is the investigator's responsibility to return or destroy all unused study supplies, as directed by the sponsor. Appropriate records of return or disposal must be maintained for accountability purposes. For the return of samples, the following address shall be used:

To: Merz North America, Inc.
Attn: Receiving
[name]
[name]

[figure not shown]
All study-accountability procedures must be completed before the study is considered complete.

[figure not shown]
6.3.7 Accountability procedures

The sponsor will provide the investigator with necessary study supplies. Accountability for study supplies at the study site is the responsibility of the investigator.

Access to investigational medical devices will be controlled, and the investigational medical devices will be used only in the clinical investigation and according to the clinical study protocol. The sponsor will keep records to document the physical location of all investigational medical devices from shipment to the investigation sites until return or disposal. The Principal Investigator or an authorized designee will keep records documenting the receipt, use, return, and disposal of the investigational medical devices, which will include:

1. The date of receipt.
2. Identification of each investigational medical device (batch number/serial number or unique code).
3. The expiry date (if applicable).
4. The date or dates of use.
5. Subject identification number.
6. Date on which the investigational medical device was returned/explanted from subject, if applicable.
7. The date of return of unused, expired, or malfunctioning investigational medical devices (if applicable).

7 SAFETY AND ADVERSE EVENTS

7.1 Definitions

7.1.1 *Investigational medical device*

An investigational medical device is defined as a medical device being assessed for safety or effectiveness in a clinical investigation. This definition includes medical devices already on the market that are being evaluated for new intended uses, new populations, new materials, and/or design changes. In this protocol, the terms “investigational medical device” and “investigational device” are used interchangeably.

7.1.2 *Adverse event (AE)*

An AE is defined as an untoward medical occurrence, which does not necessarily have a causal relationship to the investigational medical device. An AE can therefore be any unfavorable, unintended, or untoward clinical sign (including an abnormal laboratory finding), unintended disease or injury, and/or a symptom or disease temporally associated with the use of the investigational medical device, whether or not considered related to that investigational medical device.

- Definition includes events related to the investigational medical device or the comparator.
- Definition includes events related to the procedures involved.
- AEs may include, but are not limited to, subjective or objective symptoms spontaneously offered by the subject, uncovered by review of concomitant medications or therapies, and/or observed by the investigation-site staff. The investigator will determine the description (sign, symptom, or diagnosis), onset, outcome, seriousness, severity, cause, and action taken for any event.

In cases of surgical or diagnostic procedures, the condition/illness leading to such a procedure is considered as the AE, rather than the procedure itself.

Pre-existing conditions that do not worsen during the course of the clinical investigation are not reportable as AEs. Recurring symptoms associated with pre-existing conditions are not considered AEs unless they have a clinically significant increase in severity and/or frequency. To determine whether a condition has worsened, it is compared to the condition of the subject at screening.

Elective treatments planned before screening, which are documented in the subject's source data, are not typically regarded as AEs. The subject's course must be monitored

until the event has subsided, or in a case of permanent impairment, until the event stabilizes and the overall clinical outcome has been ascertained.

7.1.3 Adverse device effect (ADE)

An ADE is defined as an adverse event related to the use of an investigational medical device.

- Definition includes adverse events resulting from insufficient or inadequate instructions for use, deployment, implantation, installation, or operation, or any malfunction of the investigational medical device.
- Definition includes any event resulting from use error or from intentional misuse of the investigational medical device.

7.1.4 Serious adverse events (SAE)

A SAE is any AE that results in:

- Death
- Life-threatening illness or injury (or places the subject at immediate risk of death from this event as it occurred) or
- Hospitalization or prolonged hospitalization, or
- Disability/incapacity or permanent impairment of a body structure or a body function, or
- An important medical event for which medical or surgical intervention is required to prevent life-threatening illness or injury, or permanent impairment of a body structure or body function, or
- Fetal distress, fetal death, or a congenital abnormality/birth defect.

NOTE: Planned hospitalization for a pre-existing condition, or a procedure required by the protocol, without serious deterioration in health, is not considered a serious adverse event. Pre-planned admissions must be recorded in the subject's source documentation.

If a subject experiences an additional AE that prolongs a pre-planned hospitalization, this event is considered to be an SAE and should be reported as an SAE.

In the case of a fatality, the primary cause of death (the event leading to death) is considered as the SAE, and death is considered the outcome. "Fatal" will be recorded as the outcome. Death may be reported as an SAE only when no cause of death can be determined (e.g., sudden death, unexplained death).

7.1.5 *Serious adverse device effect (SADE)*

A SADE is defined as an SAE related to the use of an investigation medical device.

- Definition includes SAEs resulting from insufficient or inadequate instructions for use, deployment, implantation, installation, or operation or any malfunction of the investigational medical device.
- Definition includes any SAE resulting from use error or from intentional misuse of the investigational medical device.

7.1.6 *Unanticipated adverse device effect (UADE)*

A UADE is defined as:

- Any serious adverse effect on health or safety or any life-threatening problem or death caused by, or associated with, a device, if that effect, problem, or death was not previously identified in nature, severity, or degree of incidence in the investigational plan or application (including a supplementary plan or application), risk analysis report, Investigator Brochure (IB), or Instructions for Use (IFU), or
- Any other unanticipated serious problem associated with a device that relates to the rights, safety, or welfare of subjects.

7.1.7 *Anticipated serious adverse device effect (ASADE)*

An ASADE is defined as:

- Any serious adverse effect which by its nature, severity, or degree of incidence or outcome has been identified in the risk analysis report, IB, or product labeling.

7.1.8 *Common treatment responses (CTR)s*

CTRs are common clinical presentations and/or side effects that a study subject may experience following treatment. Subjects will self-report CTRs, as defined *a priori* in the protocol, on a diary provided to them. The treating investigator will review the diary and determine if any diary entries should be captured as AEs. A CTR that is more severe than what is generally expected and/or is not resolving should also be evaluated by the investigator as a possible AE or SAE. CTRs include the following: swelling; visible lumps; bumps you can feel; bruising or discoloration; redness; rash; pain/discomfort (including burning/stinging); itching; blistering/peeling skin; and/or scabby/crusty skin.

Treated subjects will be instructed (within the diary) to seek immediate medical attention if any of the following symptoms are observed: changes in vision; fever; dizziness;

confusion; weakness in arms/legs; changes in alertness/consciousness; difficulty speaking; face droop; change in skin color comparing one side to the other; a blue or white spot of skin; and/or a headache that is more intense or longer than you usually experience. They will also have the opportunity to self-report any unforeseen/unanticipated events on the diary.

7.1.9 *Device deficiency*

A device deficiency is defined as any inadequacy of a medical device with respect to its identity, quality, durability, reliability, safety, or performance. Device deficiencies include malfunctions, use errors, and inadequate labeling.

Device deficiencies include events that did not lead to an AE, but could have led to a medical occurrence if suitable action had not been taken, if intervention had not been made, or if circumstances had been less fortunate.

All device deficiencies shall be documented and reported by the PI throughout the clinical investigation and appropriately managed by Merz North America, Inc. in accordance with [Sections 7.2.4.3](#) and [7.3](#).

7.1.10 *Malfunction*

Malfunction is defined as failure of an investigational medical device to perform in accordance with its intended purpose, when used in accordance with the product labeling or the protocol.

All device malfunctions shall be documented and reported by the PI throughout the clinical investigation and appropriately managed by Merz North America, Inc. in accordance with [Sections 7.2.4.3](#) and [7.3](#).

7.2 *Reporting requirements*

7.2.1 *Determining severity/intensity*

The investigator is required to grade the severity/intensity of each AE. The clinical intensity of an AE will be classified as:

- ***Mild:*** Signs and symptoms that can be easily tolerated. Symptoms can be ignored and disappear when the subject is distracted.
- ***Moderate:*** Signs and symptoms that cause discomfort and interfere with normal functioning, but are tolerable. They cannot be ignored and do not disappear when the subject is distracted.

- **Severe:** Signs and symptoms that affect usual daily activity and incapacitate the subject, thereby interrupting his/her daily activities.

The definitions above are difficult to apply for some data (e.g., clinically relevant laboratory values that are documented and evaluated on the eCRF AE report form). In such situations, the investigator should exercise medical and scientific judgment.

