3.2.2 Safety assessments

3.2.2.1 Adverse events and common treatment responses

All AEs reported by study subjects, investigators, or other study staff after the time of informed consent through end of study will be recorded. Events will be recorded regardless of causality. Note: End of study will be 13-months from baseline treatment for subjects who receive a touch-up, 12-months from baseline treatment for subjects who do not receive a touch-up, and Month 2 for control subjects.

A subject diary will be dispensed on the day of treatment to collect CTR information as well as specific safety concerns. The diary will be collected daily for 4-weeks post-treatment. Another 4-week diary will be distributed and completed following touch-up treatment at Month 1, if applicable.

Subjects will be asked to record daily on the diary any pre-defined CTRs and other safety events that may occur. The treating investigator will review and determine if any entries should be captured as AEs. Subjects assigned to the control group will not be provided or asked to complete the diary.

After the baseline treatment, treated subjects will receive a 72-hour post-treatment phone call and return to the clinic for a 2-weeks post-injection visit. During these safety checks, the subject diary will be reviewed for potential AEs. Subjects will continue their diary for 1-month after baseline treatment. If a subject receives an optional touch-up 1-month after baseline treatment, the subject will receive a 72-hour post touch-up phone call and return to the clinical 2-weeks post touch-up. Touch-up diaries will be reviewed for potential AEs and subjects will continue to complete the diary for 1-month after the touch-up injection.

Additional information on safety assessments and procedures is discussed in [Section 7](#).

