3.2.2.2.4 Undilated central retinal fundoscopic exam using an ophthalmoscope

In this procedure, the oculoplastic surgeon will perform a focused exam of the central retina and blood vessels to evaluate for any evidence of vascular occlusion.

After the injection of the first IOH (either baseline treatment or touch-up, if applicable), subjects will be asked to wait 30 minutes and then repeat the visual safety assessments for the already treated side. The subsequent side will then be injected once these assessments are completed on the first side and the investigator confirms that it is safe to proceed with treatment on the second IOH. The subject will then receive the Belotero Balance to treat the second IOH, wait 30 minutes, and then repeat the visual safety assessments for that side. When the subject returns for the 2-week safety follow-up visit and any subsequent visits, these visual assessments will be repeated and compared to baseline for any changes that could indicate a safety signal or concern.

NOTE: If only injecting one side for touch-up, only the side being injected will need the visual safety assessments 30-minutes post-treatment.

A local retinal specialist will be identified in advance to address any visual changes and potential retinal artery occlusion (i.e., investigator-determined, clinically significant changes in vision, such as blindness, blurriness, double vision, pain in or around the eye [other than typical injection-induced pain], blind spots, or restriction of eye motility).

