7.2.4 Procedures for reporting specific events

7.2.4.1 Adverse event (AE) and adverse device effect (ADE)

Subjects will be carefully monitored during the clinical investigation for possible AEs and ADEs.

The period of observation for AEs and ADEs extends from signing of the informed consent form (ICF) until the subject’s last visit. Any medical occurrence between the

time the ICF is signed and the first treatment with the investigational medical device is classified as an AE or ADE and must be documented in the subject's file and in the eCRFs. New AEs or ADEs reported to the investigator during the observational period (i.e., after the start of treatment with the investigational medical device) must also be documented, treated, and followed.

Any AE, ADE, and/or device deficiency observed will be fully investigated, documented, and followed until the event is either resolved or adequately explained at the End of Study visit.

The investigator will assess and record any AE or ADE in detail in the subject's file (medical record) and in the eCRF AE report form. At a minimum the following information will be recorded:

- AE diagnosis or main symptom
- Location of AE: systemic or restricted to injection area. In case of local reaction, the corresponding area should be reported.
- Start and stop dates
- Severity/Intensity
- Causal relationship
- Serious (yes or no)
- Outcome
- Action taken with investigational medical device

In this study, any adverse event of visual disturbance (including, but not limited to, any loss of vision, blurry vision, double vision, pain in or around eye (other than typical injection-induced pain), blind spot or shadow in the visual field, trouble moving eyes, etc.) will be reported. The investigator will be instructed to report any AE of visual disturbance within 24 hours. The incident will then be reported to the Agency within 10 business days of receipt by the sponsor. These reports will be generated by the sponsor or designee and will include injection volume, symptoms observed, time to onset and resolution, and any interventions implemented.

7.2.4.2 *Serious adverse event (SAE) and serious adverse device effect (SADE)*

The investigator must report all SAEs and SADEs that occur during the observational period on the SAE form within 24 hours, whether considered related or not related to the investigational device.

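### The list of symptoms for which subjects must seek immediate care (Protocol 7.1.8) omits abnormal eye pain and, less importantly, trouble moving the eyes, although the protocol's own safety sections name both

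*Protocol*

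**What the plan says.** Protocol Section 7.1.8 describes two lists for treated subjects. The first is the common treatment responses (CTRs) to be logged in the diary, ten items of which one is pain or discomfort. The second is an instruction: "Treated subjects will be instructed (within the diary) to seek immediate medical attention if any of the following symptoms are observed: changes in vision", followed by fever, dizziness, five neurological signs, two skin-colour signs and an unusual headache, making 11 items in all. On unlisted events the section adds: "They will also have the opportunity to self-report any unforeseen/unanticipated events on the diary".

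Two other sections describe warning signs around the eye.

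- Section 3.2.2.2.4 requires a retinal specialist, identified in advance, to address visual changes and potential retinal artery occlusion. It describes these as "investigator-determined, clinically significant changes in vision, such as blindness, blurriness, double vision, pain in or around the eye" (typical injection pain excepted), and goes on to blind spots and restricted motility.
- Section 7.2.4.1 lists the visual disturbances the investigator must report within 24 hours. After loss of vision, blurred vision and double vision it continues: "pain in or around eye (other than typical injection-induced pain), blind spot or shadow in the visual field, trouble moving eyes".

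Section 3.2.2.1 gives the diary a wider remit than CTRs. It is there "to collect CTR information as well as specific safety concerns", and "Subjects will be asked to record daily on the diary any pre-defined CTRs and other safety events that may occur".

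**The concern.** The 7.1.8 list is where the protocol says what subjects are told to act on at once. It is narrower than the set of signs the same protocol treats as possible evidence of vascular occlusion.

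The main gap is eye pain without any visual change. Section 7.1.8 presents pain as an expected response to be logged, and the treatment area described in Section 6.3.2 lies at the lower eyelid, so ordinary injection pain is itself close to the eye. A subject with abnormal eye pain and normal sight could record it as ordinary discomfort and do nothing more.

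Time is what is at stake. For an intravascular or embolic event, Section 3.2.2.5 calls for prompt medical attention and asks the physician to consider immediate retinal referral and hyaluronidase. Section 1.2 lists permanent vision impairment and blindness among the rare serious risks of facial fillers. The investigator's 24-hour report also depends on the investigator learning of the symptom.

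**Working it through.** The plan states no figure on this point, so the check is a comparison of lists and of review intervals.

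**Comparison of lists.** The six disturbances named in Section 7.2.4.1, set against the other two sections:

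| Sign in 7.2.4.1 | In 3.2.2.2.4 | In the 7.1.8 immediate-care list |
|---|---|---|
| Loss of vision | Yes (blindness) | Covered as a change in vision |
| Blurred vision | Yes | Covered as a change in vision |
| Double vision | Yes | Covered as a change in vision |
| Blind spot or shadow | Yes (blind spots) | Covered as a change in vision |
| Trouble moving the eyes | Yes (restricted motility) | Not named; covered when double vision is present |
| Eye pain beyond typical injection pain | Yes | Not named |

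That is 4 covered, 1 partly covered and 1 not named, out of 6. Of the 11 items in 7.1.8, none refers to eye pain or eye movement. The only item that is a pain at all is the unusual headache.

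**Longest wait for a mandated review.** Windows are taken as printed in Section 5.1, with Day 0 as the injection:

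- telephone call at 72 hours ±1 day: Day 2 to 4
- Week 2, Day 14 (+3 days): Day 14 to 17
- Month 1, Day 28 (+3 days): Day 28 to 31

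Each interval runs from (earliest later review − latest earlier review) to (latest later review − earliest earlier review):

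- injection to call: 2 − 0 = 2 to 4 − 0 = 4 days
- call to Week 2: 14 − 4 = 10 to 17 − 2 = 15 days
- Week 2 to Month 1: 28 − 17 = 11 to 31 − 14 = 17 days

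After a touch-up the same three reviews repeat, so the same intervals apply. The Month 2 diary collection falls after the 28-day touch-up diary has ended and adds no longer interval.

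**Other routes by which a painful eye could come to attention.**

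- Visual examination 30 minutes after each injection (3.2.2.2.4, 5.1) covers the period just after injection, not later onset at home.
- The diary is collected daily (3.2.2.1), and under 5.1.2 an entry may prompt an unscheduled visit. However, 9.5.3 ties staff review to Sections 3.2.2.1 and 5.1, whose stated reviews are the call and the visits. No daily staff review is stated.
- Section 7.1.8 says: "A CTR that is more severe than what is generally expected and/or is not resolving should also be evaluated by the investigator". This directs the investigator once the entry is seen; it does not direct the subject.
- At the 72-hour call, a reported safety concern leads to an unscheduled visit, a specialist or emergency care (5.1).
- The consent form carries a 24-hour number for medical concerns and the retinal specialist's contact (9.2). The one example given for using the specialist contact is sudden visual change.

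These routes make same-day action possible. None is stated to tell a subject with isolated eye pain to seek care at once.

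**The case against.** The strongest reply is that the protocol itself defines the term. Section 3.2.2.2.4 gives eye pain and restricted motility as examples of changes in vision, and Section 7.2.4.1 places both under visual disturbance. Read that way, the first item of the 7.1.8 list already includes them. This is fair as a matter of drafting, but the passage in 3.2.2.2.4 concerns what an investigator determines. A subject whose eye hurts and who sees normally has little reason to read it as a change in vision.

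Second, Section 7.1.8 only describes the diary. The diary and consent form are not in the documents and may already contain the wording. This stands, and it limits the point to the list as the protocol describes it.

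Third, the three lists serve different purposes (self-referral, specialist referral, event reporting), and nothing requires them to match. This also stands: the instruction is incomplete, not contradictory. Separating abnormal from ordinary injection pain takes judgement. Yet 7.1.8 already asks subjects to make that kind of judgement about headache.

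Fourth, the 24-hour number is not limited to visual symptoms, the injectors are oculoplastic surgeons, and Section 3.2.2.2 calls serious events associated with retinal artery occlusion very uncommon. The documents give no rate for isolated eye pain and do not describe occlusion presenting as pain alone. All of this lowers the expected harm, and the longest waits arise only if every safeguard fails. It does not supply the missing instruction.

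Fifth, the eye-movement item adds little. That is accepted: it is not a CTR, it is examined at visits, and with double vision it is already covered.

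**Conclusion.** The concern holds. As described in Section 7.1.8, the immediate-care list is narrower than the warning signs in Sections 3.2.2.2.4 and 7.2.4.1. The gap that matters is eye pain without visual change; eye movement is a minor gap.

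One of the six named disturbances is missing outright and one is partly covered. With all safeguards failing, the wait for a mandated review is at most 4 days from injection, 15 days from the call, or 17 days from Week 2. These are bounds, not expected delays. About 44 treated subjects keep the diary for 28 days, and for 28 more after a touch-up.

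The conclusion assumes that the diary and consent form add nothing to what the protocol describes, and that a lay reader would not take eye pain to be a change in vision. Neither can be checked from the documents, so confidence is medium. No endpoint or analysis is affected. The correction should be made because it is specific and cheap, and because under Section 2.1 this pilot informs the design of a pivotal study.

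**What to change.** Add two items to the immediate-care list in Section 7.1.8 and to the diary: pain in or around the eye beyond typical injection pain, and trouble moving the eyes. Leave the pain or discomfort CTR item and its data capture unchanged. At most, put a note beside it in the diary pointing to the immediate-care list. If the diary already carries this wording, only the sentence in 7.1.8 needs changing.

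The cost is a small amendment (one protocol sentence plus diary text), which under Section 9.9 needs written ethics committee or review board approval and regulatory submission. Because ordinary injection pain is near the eye, expect a few extra calls or unscheduled visits for benign pain. The CTR safety endpoint is unaffected.
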